7 TRIAL ENDPOINTS

Immunogenicity will be assessed through:

- Serum anti-rotavirus IgA response (defined as a ≥3 fold increase from baseline) at each serum collection time-point to 4 weeks after 3 doses of RV3-BB.
- Serum anti-rotavirus IgA levels at each serum collection time point.
- Vaccine take defined as at least a threefold increase in serum anti-rotavirus immunoglobulin A (IgA) from baseline to post IP dosing, or detectable RV3 shedding in stools (by ELISA or PCR) any day from day three to day five following administration of IP.
- Cumulative vaccine take defined as vaccine take observed at the current assessment time point or following any previous dose.
- Anti-rotavirus IgA response (defined as at least a threefold increase from baseline to post IP dosing) at each serum collection time point.
- Anti-rotavirus IgA titres defined as geometric mean titres at each serum collection time point.
- Presence of RV3 shedding in stools (by ELISA or PCR) from day 3 to day 5 following each dose of IP.

Safety and tolerability will be assessed through:

- Adverse Events (AE) in the 28 days following each dose of IP.
- Serious Adverse Events (SAE) during the study.
- Review of episodes of blood in stool.

The exploratory objectives will be assessed through:

- HBGA Lewis and secretor status will be determined by ELISA/PCR on Saliva collected at Visits 1, 3, 5 and 7 and whole blood collected at Visit 9 for non secretor participants.
- Maternal serum IgA and IgG responses will be determined by ELISA on Maternal Serum sample collected pre study or at Visit 1.
- Bacterial taxonomic and genetic functional profiling of stool microbiome will be conducted by 16s rRNA or shotgun sequencing on maternal stool and stool samples collected post administration of IP and at birth (prior to first IP dose).
- B and T cell function will be measured by Flow cytometry and innate and adaptive responses measured by whole killed pathogen assay and Toll like receptor ligand assays from whole blood collected at birth (cord), Visit 3 and Visit 9.

8 TRIAL MEASUREMENTS AND OUTCOMES

8.1 Eligibility assessments

A full physical examination will be performed at study entry by a clinician prior to randomisation at Visit 1, according to common medical practice. The examination will include assessment of general appearance, HEENM (head, ears, eyes, nose and mouth),

skin, cardiovascular system, musculoskeletal system, respiratory system, gastrointestinal system and nervous system. Length (height) and weight will be measured. New findings or clinically significant changes noted in any physical examinations conducted post dosing will be recorded as AEs.

8.2 Immunogenicity

Faecal samples will be collected from participants following each dose of IP. One sample will be collected during the day 3-5 post dose period. These samples will be tested at the study central laboratories for shedding of rotavirus.

Serum samples will also be tested at the central laboratories, for anti-rotavirus IgA.

See Section 8.6 for testing at each laboratory.

Faecal and serum samples collected for this study may be stored for up to 4 years poststudy, and if consent has been obtained from the parents/guardians, may be used for additional testing outside of this protocol. Stored samples will be labelled with the participants study number. Any additional testing would be performed under a protocol approved by an ethics committee, and would maintain strict confidentiality.

8.3 Safety

Safety will be assessed by recording of AEs, vital signs, and occurrence of blood in stool throughout the study.

- Parents/guardians will be questioned and monitored throughout the study with regard to any AEs their baby may have experienced. See Section 11 for further details on recording AEs.
- Vital signs will be measured at each site visit and will include pulse rate, respiratory rate and temperature.
- Parents/guardians will be issued with thermometers and will be instructed on how to take the participant's axillary temperature, which should be measured and recorded if the baby has a diarrhoea episode.
- Parents/guardians will be instructed to immediately contact study staff if the participant has any episode of blood in stool during the study. A doctor will assess the participant for each case of blood in stool. An abdominal ultrasound may be conducted, including if intussusception is suspected. Blood in stool and any ultrasound findings will be recorded as AEs.

8.4 Diarrhoea capture

Incidence of diarrhoea will be assessed by recording and grading of diarrhoea episodes during the study. For this study the definition of diarrhoea is three or more stools in a 24 hour period that are looser than normal for that child.

A Diarrhoea Log will be completed by the parents/guardians throughout the study. For each diarrhoea episode the date, participant's temperature, time of first and last loose stool of the diarrhoea episode, number of loose stools in each 24-hour period, time of first and

last vomit of any vomiting associated with the diarrhoea episode, and number of vomits in each 24-hour period will be recorded.

Parents/guardians will be instructed to contact the study staff to notify them of each episode of diarrhoea. The study staff will record the participant's symptoms, including degree of dehydration, treatment, duration of illness and outcome.

Two faecal samples should be collected per diarrhoea episode, from separate stools. Faecal samples will be tested at the study central laboratories for presence and strain of rotavirus. Instructions for sample collection, transport, processing and storage are contained in the SRM.

The details of the diarrhoea episode will be scored in the study database using a modified version of the Vesikari clinical score for gastroenteritis in infants (Appendix 1).

Episodes of diarrhoea will also be recorded as AE.

Analysis of separate faecal samples by stool microscopy and stool culture for identification of an underlying causative agent besides rotavirus may be done in the hospital or MLW Laboratory, Blantyre for cases where a participant is admitted to hospital with diarrhoea (or for other cases if clinically indicated or if requested by the investigator and/or Medical Monitor).

See Section 8.6 for testing at each laboratory.

8.5 Exploratory

A saliva sample will be collected from participants at Visit 1. The sample will be tested at the laboratory to determine the Lewis and secretor histo-blood group antigen status. A saliva sample will be collected at all IP dosing visits, to determine the phenotypic expression of the Lewis and secretor histo-blood group antigen status of participants.

The maternal serum sample will be tested for serum IgA as per Section 8.2, and for antirotavirus IgG.

Bacterial taxonomic and genetic functional profiling of stool microbiome will be conducted on a maternal stool sample and stool samples collected post administration of IP and at birth (prior to first IP dose) by 16S and shotgun sequencing. Assessment of T cell and B cell function will be completed by flow cytometric assays on whole blood (cord blood, Week 6 and Week 18). Innate and adaptive immunity will be assessed by *in vitro* reactivity in toll-like receptor ligand assays and whole killed pathogen assays by measurement of cytokines in supernatants collected from whole blood cultures with TLR agonists and whole killed pathogens.

See Section 8.6 for testing at each laboratory.

8.6 Central laboratories

Central laboratories for this study, and the tests they are performing, are;

- MLW Laboratory, Blantyre, Malawi:
 - Immunogenicity endpoints: shedding of rotavirus in post dose stool samples.

- Diarrhoea endpoint: presence and strain of rotavirus in diarrhoea samples.
- Exploratory endpoints: Lewis and secretor histo-blood group antigen status and phenotypic expression from saliva sample and whole blood.
- T and B cell function from cord and blood samples, and innate and adaptive immunity from cord and blood samples.
- Enteric Viruses Research Laboratory, MCRI, Melbourne, Australia
 - Immunogenicity endpoints: sequence analysis of faecal samples for shedding, and serum sample (including maternal) testing for immunogenicity.
 - Exploratory endpoints: IgA and IgG in maternal serum sample, maternal and stool microbiome testing and cytomegalovirus and Epstein-Barr virus testing of serum for the assessment of the immune development exploratory endpoint.

Instructions for sample collection, transport, processing and storage are contained in the SRM.

9 CONCOMITANT MEDICATIONS AND VACCINES

9.1 Concomitant medications

All prescription and non-prescription medication including traditional, herbal and complementary medicines given to the participant from birth until end of study will be recorded.

In addition, prescription and non-prescription medication including traditional, herbal and complementary medicines taken by the mother will be recorded from 4 weeks prior to delivery, during delivery, and post-delivery until end of study (or until cessation of breastfeeding).

Concomitant medications records will include the drug name, total daily dose, route of administration, start and stop date of administration, and indication (for participants only).

9.2 Routine Concurrent Vaccines

During the study period, all trial participants should continue to receive standard EPI immunisations in accordance with the routine schedule and local recommendations, with the following exceptions;

- All study participants will be administered IPV by study staff at weeks 6, 10 and 14, rather than OPV, as a transition from OPV to IPV in Malawi is planned during the period of the trial
- Participants will not receive the standard Rotarix® schedule of vaccines during the study. As RV3-BB vaccine efficacy is not yet established, all participants will be administered a single dose of Rotarix® approximately one month after their final dose of IP.

Additional licensed vaccines may be administered as appropriate for the participant.

Commercial name, batch number, and date of administration will be recorded for all vaccinations.

10 INVESTIGATIONAL PRODUCT

The RV3-BB Rotavirus Vaccine and placebo will be manufactured, packaged and labelled by Meridian Life Sciences, USA.

Table 2: Identity of IP

Name:	RV3-BB Rotavirus Vaccine	Placebo
Formulation:	 Each dose is a cell free solution containing attenuated rotavirus particles High dose at a concentration of 1.0 x 10⁷ FFU/ml) in 10% sucrose/cell culture medium. Mid dose at a concentration of 3.0 x 10⁶ FFU/ml) in 10% sucrose/cell culture medium. Low dose at a titre of 1 x 10⁶ FFU/ml) in 10% sucrose/cell culture medium. 	Sterile solution of cell culture medium and 10% sucrose
Route of administration:	Oral	Oral
Dosage:	1 mL	1 mL
Dosage form:	Single dose sterile aqueous solution for oral administration	Single dose sterile aqueous solution for oral administration

10.1 Special Warnings and Precautions for use of IP

RV3-BB Rotavirus Vaccine

Please see the Investigator Brochure for detail.

Based on data preclinical animal testing, the two clinical trials of the first generation RV3 Rotavirus Vaccine, and data from the RV3-BB clinical trials conducted to date (Danchin et al, 2013, Bines et al, 2015), side effects from RV3-BB candidate could include gastrointestinal events (for example: vomiting, diarrhoea/loose bowel motions and abdominal discomfort).

Although no previous recipient of either the first or second generation RV3 Rotavirus Vaccine experienced an anaphylactic reaction there is a low risk of a generalised anaphylactic reaction to the IP.

As for any study in neonates, particularly in low-income settings, the Investigator should be aware of the following:

• Jaundice is not uncommon in the neonatal period and is usually self-limited often occurring in association with establishment of breast feeding. Jaundice was observed in infants in both the vaccine and placebo groups in the Phase IIa and IIb clinical trials of the RV3-BB vaccine

• Sepsis is an important cause of death and illness in the neonatal period, particularly in low income settings. Neonatal Sepsis occurred in infants in both the neonatal and infant vaccine schedule in the Phase IIa and IIb study.

In the phase IIb study, one participant developed intussusception, although this was 114 days after the final dose of IP. As intussusception is a known rare side-effect of other rotavirus vaccines, the cautious approach is to assume it may be a class effect and parents/guardians will be advised of potential symptoms of intussusception.

Placebo

The Placebo contains only cell culture medium and 10% sucrose. There are no known warnings or risks associated with the use of the Placebo.

10.2 Labelling and Packaging

IP will be supplied as 1 mL single doses in prefilled plastic cryovials, which will be packed and stored in bulk outer boxes. Each box of IP will contain up to 81 vials of either RV3-BB or placebo.

The IP will be labelled according to local legal requirements and GMP guidelines.

Syringe labels

IP will be thawed and drawn into polypropylene syringes for dispensing and administration. The syringe will be labelled by the pharmacist indicating protocol number, randomisation number, date and time of thawing, and time by which IP must be administered (expiry time).

10.3 Storage requirements

Vaccine and placebo vials will be stored at $-70^{\circ}C \pm 10^{\circ}C$ in a temperature-monitored and alarmed freezer. The IP will be stored in a secure and access-restricted location, isolated from any potential sources of contamination.

Once thawed, IP must not be refrozen but may be stored at 2-10°C for a maximum of 6 hours until time of administration.

Following removal from 2-10°C storage, the IP should be administered as soon as possible, within a maximum of 20 minutes at room temperature.

10.4 IP accountability

All material supplied is for use only in this clinical study and should not be used for any other purpose.

The PI or designee is responsible for IP accountability, reconciliation and record maintenance. The PI or designated site staff must maintain IP accountability records throughout the course of the study including records of the amount of IP received, the identification of the participant for whom it was dispensed, and the date(s) and quantity of the IP dispensed.

The IP and records must be available for inspection by a study monitor during the study. IP supplies, including unused, partially used or empty vials and syringes, must be retained and will either be returned by the site to MCRI or designee, or destroyed on site if written approval to do so is given by MCRI and appropriate facilities and procedures are available. Records shall be maintained by the PI of any disposition of the IP. These records must show the identification and quantity of IP disposed of, the method of destruction, and the person who disposed of the IP.

10.5 Doses and treatment regimens

Approximately 688 participants will be prospectively randomised to one of the following four treatment groups in a 1:1:1:1 ratio.

- High dose neonatal RV3-BB vaccine schedule (1x10⁷titre dose). RV3-BB Vaccine for doses 1, 2 and 3 and placebo for dose 4
- Mid dose neonatal RV3-BB vaccine schedule (3x10⁶titre dose). RV3-BB Vaccine for doses 1, 2 and 3 and placebo for dose 4.
- Low dose neonatal RV3-BB vaccine schedule (1x10⁶titre dose). RV3-BB Vaccine for doses 1, 2 and 3 and placebo for dose 4.
- High dose Infant RV3-BB vaccine schedule (1x10⁷titre dose). Placebo for dose 1 and RV3-BB Vaccine for doses 2, 3 and 4

Participants will also receive a dose of commercially available Rotarix® at 18 weeks of age.

10.6 Method for Assigning Participants to Treatment Group

Participant eligibility will be established before randomisation. Eligible participants will be assigned to a treatment arm according to the randomisation schedule.

At each site, a unique Screening Number will be allocated to each pregnant woman who provides preliminary informed consent, so that potential participants can be identified without making assumptions about their subsequent eligibility for the main trial. From birth, the baby will have the same Screening Number as their mother.

Randomisation will be stratified by birth multiple (single vs multiple), to minimise imbalance across the treatment arms. Multiple births will be randomised to the same treatment arm to avoid potential contamination across treatment arms.

Eligible participants will be randomised at V1 following confirmation of eligibility. The pharmacist will assign the next available Randomisation Number and prepare the IP dose.

The Randomisation Number will be used to identify the participant throughout the study period and on all study-related documentation.

If study consent is not given, or a participant fails screening, the Screening Number will not be reused. If a participant is discontinued after randomisation, the Randomisation Number will not be reallocated.

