5.2.3 Inclusion Criteria

- Neonate is less than 6 days (≤ 144 hours) of age at the time of first dose.
- Neonate is in good health as determined by clinical judgment, including a medical history and physical exam, which confirms the absence of a current or past disease state considered significant by the investigator.
- Neonate birth weight 2500-4000g inclusive or 2250-4000g inclusive at Visit 1.
- Neonate's parents/guardians expect to be available for the duration of the study, and agree to adhere to all protocol requirements.
- Neonate's parents/guardians have provided written informed consent prior to study-related procedures being performed.

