7.1.3 Stratifications

For analysis purposes, participants may be sub-classified into the following stratification levels, where applicable:

- Gender
 - o Male
 - \circ Female
- Delivery route
 - o NVD
 - Caesarean Section
- Race/predominant ethnicity
 - o American Indian or Alaska Native
 - o Asian
 - Black or African American
 - Native Hawaiian or Other Pacific Islander
 - o White
 - o Other
 - o **Unknown**
 - Not reported

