The difference between high and low titre arms in the response rate and its 95% confidence interval will be calculated. The cumulative probability of anti-rotavirus serum IgA response (as defined above) by 18 weeks of age will be estimated by the Kaplan-Meier method for each vaccine arm. PROC LIFETEST (SAS[®] Version 9.4 or above) will

be used to analyse the response rates (non-responder *vs.* responder). With the CENSOR variable, 1 is commonly used to indicate that an event occurred (subject is a responder) and 0 indicates that the event did not occur (the subject was censored/is a non-responder).

Non-inferiority of the lower titre vaccine will be demonstrated if the upper bound of the confidence interval is below 20%.

Additionally, we will calculate the 95% CI of the difference between vaccine groups in the serum IgA response rate after dose 3 using the method of Newcombe-Wilson without continuity correction for the difference between binomial proportions as implemented in PROC FREQ (SAS® Version 9.4 or above).

Generalized estimating equations (GEE) will be used to analyse the response rates (non-responder vs. responder) after dose 3 using PROC GEE (SAS® Version 9.4 or above). We will calculate a binary outcome ($1 = \ge 3$ -fold increase, 0 = < 3-fold increase from baseline) after dose 1, 2, and 3 for each participant who received vaccine according to the neonatal schedule. After that, we will fit a model with dose as a discrete/categorical/factor variable, vaccine group (low, medium, high dose) as a discrete variable, and dose by vaccine group interaction term. The model will use the binomial distribution for the outcome variable and the exchangeable correlation matrix to account for the correlation between a participant who received vaccine according to the neonatal schedule outcomes. Model will be used for the analysis. Once the model is fit, contrast statements will be used in PROC GENMOD (SAS® Version 9.4 or above) to calculate the difference in the response rate after dose 3 for the high versus low dose and so forth.

In the table, (Estimate, standard error, 95% CI) will be presented.

The general linear model to be fit by GEE is

 $logit(p_{ij}) = \beta_{ij}$

where p_{ij} is the response rate after the i-th dose in the j-th vaccine group. Differences between the β s represent the log odds ratio in response rates.

MCRI-RV3-BB-004

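### Siblings from multiple births share an arm by design, but the non-inferiority analyses treat them as independent, so the intervals are slightly too narrow

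*Protocol*

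**What the plan says.** On allocation, Protocol 10.6 gives one stratification factor: "Randomisation will be stratified by birth multiple (single vs multiple), to minimise imbalance across the treatment arms". It then keeps siblings together: "Multiple births will be randomised to the same treatment arm to avoid potential contamination across treatment arms". The same section supplies a family identifier: "From birth, the baby will have the same Screening Number as their mother". Multiples are not excluded. The criterion most likely to limit their number is weight (Protocol 5.2.3): "Neonate birth weight 2500-4000g inclusive or 2250-4000g inclusive at Visit 1".

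On analysis, SAP 9.1.2 plans three methods for the serum IgA response and applies them in the same way to vaccine take and its components:

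- The cumulative probability of response "will be estimated by the Kaplan-Meier method for each vaccine arm". The 20% rule is stated for the resulting difference.
- An interval for the difference in response after dose 3, "using the method of Newcombe-Wilson without continuity correction for the difference between binomial proportions as implemented in PROC FREQ".
- A GEE on the logit scale with dose, vaccine group and their interaction, and "the exchangeable correlation matrix to account for the correlation between a participant who received vaccine according to the neonatal schedule outcomes".

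The SAP does not mention multiple births, siblings or the randomisation stratum. The sample size text (Protocol 13.1, SAP 8.1.1) has no allowance for clustering.

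**The concern.** A twin pair sent to one arm is a small randomised cluster. The siblings share a mother and can be expected to share much of the household exposure, breast milk and genetic background. Protocol 3.3 lists maternal and breast-milk antibodies, the microbiome, nutrition and histo-blood group status among the suspected reasons for poor vaccine response. Co-allocation is itself justified by possible contamination between siblings. Positive correlation within pairs is therefore plausible.

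None of the three methods allows for it. Kaplan-Meier by arm and Newcombe-Wilson assume independent infants. The GEE correlation is there to link one infant's outcomes after doses 1, 2 and 3, so two siblings would still be two independent clusters. The SAP names no clustering variable and the sentence is garbled, but participant-level clustering is its natural reading.

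Non-inferiority is declared when an upper confidence bound falls below 20%. A standard error that is too small pulls that bound down and so favours the lower titres.

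**Working it through.** **1. The plan's own sample size.** Inputs from SAP 8.1.1: 50% response in both arms, margin 0.20, one-sided 0.025, power 90%, 30% lost from the per-protocol (PP) set.

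Evaluable n per arm = (1.960 + 1.282)² × (0.25 + 0.25) / 0.20² = 131.3, so 132. Then 132 × 1.3 = 171.6, so 172 per arm, as stated. This match uses the unpooled variance; the score-test formula gives 129, and 168 after the same inflation. No version needs a design effect, so the calculation assumes independent infants.

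**2. Reference precision.** 172 × 0.7 = 120 evaluable per arm. The 95% half-width at 50% response is 1.96 × √(0.5/120) = 12.65 points.

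**3. Effect of pairs.** Let f be the share of analysed infants in complete pairs and ICC the within-pair correlation. An arm of n infants has fn/2 pairs, and each pair adds a covariance of 2 × ICC × p(1 − p). The variance of the arm total is n p(1 − p)(1 + f × ICC). The design effect is 1 + f × ICC and the standard error rises by its square root. Neither f nor ICC is in the documents; both are assumed.

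| f | ICC | Design effect | SE multiplier | Half-width (points) | Nominal one-sided error |
|---|---|---|---|---|---|
| none | – | 1.000 | 1.000 | 12.65 | 0.0250 |
| 2% | 0.3 | 1.006 | 1.003 | 12.69 | 0.0253 |
| 4% | 0.5 | 1.020 | 1.010 | 12.78 | 0.0262 |
| 6% | 1.0 | 1.060 | 1.030 | 13.03 | 0.0285 |
| 10% (stress case) | 1.0 | 1.100 | 1.049 | 13.27 | 0.031 |

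The error column is 1 − Φ(1.960 / SE multiplier). Score-test power at 120 per arm (normal approximation) is 88.1% with no pairs, 87.4% in the 4% / 0.5 case and 84.9% in the stress case.

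**4. What that means for the decision.** With the simple half-width at 50% response, non-inferiority is declared for an observed difference below 20 − 12.65 = 7.35 points. At f = 6% and ICC = 1.0 the limit becomes 20 − 13.03 = 6.97 points. The window of about 0.4 points is smaller than one infant's response in one arm (1/120 = 0.83 points).

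**5. Simulation of the Newcombe-Wilson rule.** 120 per arm, 400,000 replicates per scenario; error at true rates of 60% versus 40%, power at 50% in both arms.

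| Infants in pairs | ICC | Error | Power |
|---|---|---|---|
| none | – | about 0.028 | 89.0% |
| 5% | 0.5 to 1.0 | 0.030 to 0.032 | 88.6% to 88.4% |
| 10% | 0.5 to 1.0 | 0.032 to 0.035 | 88.4% to 87.9% |

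**6. The stratum.** If multiples are a share f of infants and their response differs by D, the stratum explains f(1 − f)D²/0.25 of the outcome variance. For f = 4% and D = 0.10 this is 0.15%; for f = 10% and D = 0.30 it is 3.2%. Leaving out a factor that was balanced by design tends to overstate the standard error, so this omission runs in the conservative direction.

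**The case against.** The strongest reply is that this cannot matter in practice. The effect is a fraction of a point against a 20-point margin, and both drivers are assumed. The top of the main range needs every pair to respond identically. Both siblings must meet the weight criterion and both must remain in a PP set expected to lose 30%; a sibling analysed alone adds no clustering. If exclusions within a pair were independent, 6% of randomised infants in pairs would become 6% × 0.7 = 4.2% of the PP set (more if siblings leave together). In the simulation, Newcombe-Wilson error is already about 0.028 with no twins, so the choice of method costs about as much as a few per cent of pairs. All of this stands, and it keeps the point minor. It does not make the independence assumption right for the allocation used.

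Three stronger readings are tempting, and the documents do not support them:

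- A reader might infer that every planned analysis is affected. The point covers the inferential immunogenicity analyses only. Safety has no formal testing (SAP 7.1.4), and the microbiome and immune-development analyses are left to separate plans (SAP section 5).
- A reader might infer that ignoring the stratum also narrows the intervals. It usually has the opposite effect, and a small one.
- A reader might take the absence of multiplicity from SAP 7.1.3 as an error. That list opens with "For analysis purposes, participants may be sub-classified into the following stratification levels, where applicable". It is an optional set of subgroups, not a record of randomisation strata or model terms. Multiplicity there would give a subgroup of about 2 to 7 evaluable infants per arm (2-6% of 120).

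**Conclusion.** The point holds as a minor one. Siblings are allocated as a unit, and the Kaplan-Meier, Newcombe-Wilson and GEE analyses do not reflect it. The standard error is understated by about 0.3-3% if 2-6% of analysed infants are in complete pairs and the ICC is 0.3-1.0, or at most about 0.4 points on a 12.65-point half-width. The weight criterion and PP losses push towards the low end. The direction favours non-inferiority, but a conclusion would change only if the bound lay very close to 20%. A reader might infer that a non-inferiority finding from this trial would be unsafe; nothing in the documents supports that. Ignoring the stratum is a separate omission, usually slightly conservative.

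**What to change.** - **GEE:** use the mother's Screening Number as the cluster for the robust standard error, so that siblings and each infant's repeated outcomes fall in one cluster. The planned model is logit and its contrasts are log odds ratios. The dose-3 risk difference therefore needs an identity link, or standardisation from the logit model with a delta-method interval.
- **Kaplan-Meier and Newcombe-Wilson:** changing the GEE leaves these two differences uncorrected. Add a bootstrap that resamples mothers, or a sensitivity analysis with one infant per mother.
- **Reporting:** give the number of sibling sets per arm in each analysis set and state how they were handled.
- **Stratum:** adjust for single versus multiple birth only if there are enough multiples for a stable estimate. At 2-6% there would be roughly 7 to 22 evaluable infants across the three neonatal arms. No change to SAP 7.1.3 is needed.

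The cost is a little more programming than a changed clustering variable. No new data are needed, because Protocol 15.11 already has participants identified in the database by Screening Number.
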